**Planned Dose Cohorts and Enrollment Table 5-1:** 

#### 5.7 Criteria for Dose Escalation, Dose Modification or Discontinuation of **Study Drug**

#### 5.7.1 **Dose Escalation Procedures**

The initial dose of ALN-TTR02 is 10 µg/kg. Dose escalation to 50, 150, and 300 µg/kg is planned.

Within each of the cohorts, the first patient will receive their first dose and if the dose is well tolerated, per Section 5.7.3 (Dose-limiting Toxicity), Patients 2 and 3 will receive their first dose at that same dose level no sooner than 48 hours apart, with Patient 2 receiving a dose of study drug no sooner than 48 hours after the dosing of Patient 1. Similar to the first dose, the second dose will be administered to patients 4 weeks after the first dose in a sequential manner with at least 48 hours separating dosing of each patient. If after the first dose, ALT and AST are > 2.5 x ULN, that patient would not receive their second dose. Dose escalation to the next cohort will proceed after the collective safety and tolerability data through at least 96 hours post-first dose from the 3 patients in the previous cohort has been reviewed by the SRC. If the administered dose is found to be safe and well tolerated, dosing for the next cohort will begin no sooner than 96 hours after Patient 3 has safely received dose 1 from the previous cohort. Patients in the cohort would be dosed and reviewed for safety and tolerability following the same procedures as used for other cohorts (as stated above).

Up to 5 optional cohorts may be included to confirm the safety, tolerability, and/or PD effect of previously evaluated dose levels, which may include evaluation of the original dosing regimen (once every 4 weeks), an alternative dosing regimen (once every 3 weeks), and/or an alternative premedication regimen and infusion rate at a specific dose of ALN-TTR02. Dosing in these optional cohorts may occur at a previously tested dose that was found to be safe and where stopping rules were not met or at an intermediate dose level. Each optional cohort will be comprised of 3 patients.

For patients on all dose levels other than the starting dose level of  $10 \mu g/kg$ , prior to receiving the second dose the SRC will review the cumulative safety and tolerability data of at least 2 patients from the previous dose level(s) with at least 96 hours of follow-up after receiving a second dose of study drug.

The dosing of patients within each of the first 4 cohorts is depicted in

[figure not shown]

.

[figure not shown]

Figure 5-1: Scheme for Patient Enrollment and SRC Review Within and Between Each Patient Cohort

#### A. First Dose

### B. Second Dose (4 weeks after first dose)a

- a Some optional cohorts may have the second dose of ALN-TTR02 administered 3 weeks after the first dose.
- b Dosing of next cohort will follow the same schema as outlined in A with the next higher dose level.

Dose-limiting toxicities are described further in Section 5.7.3, and study stopping rules are described in Section 5.7.4.

### **5.7.2** Optional Cohorts

Based on the interim evaluation of safety data, it may also be decided by the SRC that an optional cohort may be utilized which will include 3 additional patients. Dosing in these optional cohorts may occur at a previously tested dose that was found to be safe and where stopping rules were not met or at an intermediate dose level. Patients in the optional cohort would be dosed and reviewed for safety and tolerability following the same procedures as used for other cohorts. The optional cohort would be included to further confirm the safety and/or PD effect of previously evaluated dose levels, which may include evaluation of the original dosing regimen (once every 4 weeks), an alternative dosing regimen (once every 3 weeks), and/or to evaluate an alternative premedication regimen and infusion rate. The dosing regimen for the first optional cohort will be once every 4 weeks, and the dosing regimen for the remaining 4 optional cohorts will be once every 3 or 4 weeks. It is anticipated that the first 2 optional cohorts will use the original premedication regimen, and the remaining 3 optional cohorts may be used to explore the alternative premedication regimen and infusion rate. The SRC will review all available safety data and make recommendations on dosing and premedication regimens prior to dosing of any of the optional cohorts. If this occurs, the IECs will be informed of the implementation of optional cohorts. Up to 5 optional cohorts of 3 patients each are permitted in this study.

# **5.7.3 Dose-limiting Toxicity**

A DLT is defined as:

- Any life-threatening toxicity;
- ALT and AST levels  $\geq 5 \times ULN$  or total bilirubin  $\geq 2.0 \text{ mg/dL}$ ;
- An infusion reaction that requires hospitalization, despite premedication;
- Any other toxicity which in the opinion of the SRC would have precluded further dosing.

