Safety Assessments:	26. Safety evaluations will include assessment of adverse events (AEs), electrocardiograms (ECGs), cardiac monitoring (telemetry), arterial oxygen saturation (SaO 2 ) using pulse oximetry, vital signs (blood pressure, pulse rate, oral body temperature, and respiration rate), clinical laboratory safety tests (hematology, serum chemistry, liver function tests, thyroid function parameters, serology, coagulation parameters, urinalysis, cytokines, C-reactive protein, complement factors), and physical examinations.
Other Assessments:	

27. Exploratory effects of ALN-TTR02 will be evaluated by:

28. Serial measurement of circulating mutant and wild type TTR levels

	
 
29. Serial measurement of circulating vitamin A and retinol binding protein (RBP) levels
 
Blood collections to explore the expression of hepatocyte derived proteins to further characterize the biological effects of siRNA LNPs.
 

Amendment 2.1 Confidential Page 15 of 116

Dose-Limiting	Dose-limiting toxicities will include any of the following:	
Toxicities and Stopping Criteria:	1. Any life-threatening toxicity.	
Stopping Criteria.	2. ALT and AST ≥5 × ULN or total bilirubin >2.0 mg/dL.	
	3. An infusion reaction that requires hospitalization, despite premedication.	
	4. Any other toxicity which in the opinion of the SRC precludes further dosing.	
	Stopping Rules:	
	For any DLT, accrual to that dose level will stop, all dosing will be discontinued, and dose escalation will end, pending further evaluation of all available safety data by the SRC.	
Statistical Methods:	Statistical analyses will be primarily descriptive in nature.  Adverse event summaries will include tabulations of all treatment-emergent AEs, treatment-related AEs, serious adverse events (SAEs), discontinuations due to AEs, and AEs of various grading severity. By-patient listings will be provided for deaths, SAEs, and AEs leading to discontinuation of treatment.	
	Descriptive statistics will be provided for clinical laboratory data, vital signs data, and ECG interval data, presented as both actual values and changes from baseline relative to each onstudy evaluation. Laboratory shift tables from baseline to worst values will be presented.	

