#### 3 STUDY PLAN

#### 3.1 Overall Design

Protocol ALN-TTR02-002 is a multi-national, multi-center, Phase 2, open-label, multi-dose, dose escalation study designed to determine the safety, tolerability, PK, and PD of 2 consecutive doses (separated by approximately 4 weeks) of ALN-TTR02 in patients with ATTR.

Patients of any mutant TTR genotype with a biopsy-proven diagnosis of ATTR who exhibit documented signs/symptoms of the disease (e.g., sensory, motor, or autonomic neuropathy) that are at least mild to moderate in severity will be eligible for the study, provided they have a body mass index (BMI) of 17-33 kg/m², an adequate performance status (Karnofsky performance status of 60% or greater; see Appendix 3), adequate hepatic and renal function, no active infection or inflammatory disorder, stable cardiac status, and have not had a liver transplant.

Two doses, separated by 4 weeks, of ALN-TTR02 (10, 50, 150, and 300  $\mu$ g/kg) will be investigated in 4 sequential cohorts comprised of 3 patients each. No patients will be a member of more than 1 treatment group. An alternative dosing regimen of 2 doses of ALN-TTR02 (at a dose previously determined by the SRC to be safe and tolerable) separated by 3 weeks may be evaluated in the optional cohort(s).

Within each of the cohorts, the first patient will receive their first dose and if the dose is well tolerated (per Section 5.7.3, Dose-limiting Toxicity), Patients 2 and 3 will receive their first dose at that same dose level no sooner than 48 hours apart, with Patient 2 receiving a dose of study drug no sooner than 48 hours after the dosing of Patient 1. Similar to the first dose, the second dose will be administered to patients 4 weeks after the first dose in a sequential manner with at least 48 hours separating dosing of each patient. If after the first dose, ALT and AST are > 2.5 x ULN, that patient would not receive their second dose.

Dose escalation to the next cohort will proceed after the collective safety and tolerability data through at least 96 hours post-first dose from the 3 patients in the previous cohort has been reviewed by the SRC. If the administered dose is found to be safe and well tolerated, dosing for the next cohort will begin no sooner than 96 hours after Patient 3 has safely received dose 1 from the previous cohort. Patients in the cohort would be dosed

and reviewed for safety and tolerability following the same procedures as used for other cohorts (as stated above).

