#### 5.7.4 Stopping Criteria

For any DLT, accrual to that dose level will stop, all dosing will be discontinued, and dose escalation will end, pending further evaluation of all available safety data by the SRC.

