# 12 APPENDICES

### **Appendix 1:** Guidelines for Acute Infusion-Related Reactions

#### Mild or Moderate Reaction

In the event of mild or moderate symptom(s) and/or sign(s) discontinue infusion and treat as below:

- Medication as clinically indicated (e.g., paracetamol, additional H1/H2 blocker, nonsteroidal anti-inflammatory [NSAID], small volumes of physiological saline, and/or ≤5 L/min oxygen or the reaction is classified as severe);
- Re-challenge with slower infusion rate (no greater than 3 hour duration) after resolution of the reaction;
- If reaction recurs with re-challenge this patient, this will be a DLT and the patient will receive no further study drug.

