#### **Severe Reaction**

In the event of severe sign(s) and symptom(s) discontinue infusion and treat as below:

- Medication as clinically indicated (e.g., fluids [>1 L saline], oxygen [>5 L/min], adrenaline, glucocorticoids, H1/H2 blocker);
- If a severe acute reaction occurs in any patient, this is a DLT and no more patients will be dosed;

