#### **Severe Reaction**

Severe symptom(s) and/or sign(s):

- Requiring more intensive intervention than for moderate reaction with fluids (>1 L saline), oxygen (> 5L/min), and/or glucocorticoids;
- If severe reaction occurs in any patient, this is a DLT and no more patients will be dosed;

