## **Life-Threatening Reaction**

• If a life-threatening reaction occurs in any patient, this is considered a DLT and no further patients will be dosed.

Amendment 2.1 Confidential

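### Appendices 1 and 2 create automatic infusion-reaction DLTs that Section 5.7.3 and the synopsis do not list, and the stated consequence of a DLT differs between passages

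*Protocol*

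**What the plan says.** Protocol Section 5.7.3 is worded as a definition and gives four criteria: life-threatening toxicity, a liver criterion, "An infusion reaction that requires hospitalization, despite premedication", and a residual category that depends on the SRC's opinion. The synopsis carries the same infusion-reaction criterion and words the residual category as "Any other toxicity which in the opinion of the SRC precludes further dosing".

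Appendix 1 (acute reactions) says of a mild or moderate reaction: "If reaction recurs with re-challenge this patient, this will be a DLT and the patient will receive no further study drug". Of a severe one it says: "If a severe acute reaction occurs in any patient, this is a DLT and no more patients will be dosed". Appendix 2 (delayed reactions) says: "If severe reaction occurs in any patient, this is a DLT and no more patients will be dosed". Both appendices say of the most serious class: "If a life-threatening reaction occurs in any patient, this is considered a DLT and no further patients will be dosed".

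Section 5.7.4 gives the consequence of any DLT. Accrual to the dose level and all dosing stop, and "dose escalation will end, pending further evaluation of all available safety data by the SRC". Section 3.1 sets the within-cohort condition: "if the dose is well tolerated (per Section 5.7.3, Dose-limiting Toxicity), Patients 2 and 3 will receive their first dose". Section 5.7.1 and SAP Section 1.2.1 repeat it.

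**The concern.** Two questions should each have one answer in a dose-escalation protocol: is this event a DLT, and what happens next? For infusion reactions, the answer here depends on the page consulted.

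The practical exposure is between Patient 1 and Patient 2. The text schedules no SRC review at that point; it asks whether Patient 1 tolerated the dose by the Section 5.7.3 standard. Suppose Patient 1 has a severe reaction that is not life-threatening. Appendix 1 stops dosing of further patients. Yet the reaction is not itself on the list the condition cites, unless it required hospitalization or the SRC is convened and judges it a DLT. Sites could classify the same event differently and act differently before the next infusion.

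DLT status is used elsewhere too. It is a withdrawal reason by reference to Section 5.7.3 (Section 4.5.1), it bears on which doses optional cohorts may reuse (Section 5.7.2), and it is a reported safety outcome in the SAP (Sections 1.2.5.2 and 4.5.2, Table 14.3.2.4). Apart from pointing to protocol Section 5.7.3, the SAP gives no DLT definition.

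**Working it through.** The plan states no figure that this point has to reproduce. The check is a side-by-side reading of the current text, followed by simple arithmetic for scale.

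**Step 1. Is the reaction a DLT?**

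| Reaction | Section 5.7.3 and synopsis | Appendices |
|---|---|---|
| Life-threatening | Yes | Yes (Appendices 1 and 2) |
| Severe acute | Not listed; only through hospitalization or SRC opinion | Automatic (Appendix 1) |
| Severe delayed | Not listed; same two routes | Automatic (Appendix 2) |
| Mild or moderate acute, recurring on re-challenge | Not listed; same two routes | Automatic (Appendix 1 only) |

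Three reaction types are therefore automatic DLTs in the appendices and absent from both lists. The synopsis and main text mention severe infusion reactions in five places: the synopsis dosage entry and Sections 3.1, 5.6, 5.11 and 6.3.1.2. Each says study drug is not resumed. None calls the reaction a DLT.

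**Step 2. Does the hospitalization criterion close the gap?** Not reliably. Appendix 2 grades a delayed reaction as severe by the treatment it needs (fluids, oxygen, glucocorticoids), and Section 8.7 grades severity by incapacity. Neither requires admission. Under Section 5.6 every patient is already an inpatient for at least 24 hours after each infusion, so such treatment could fall within the planned stay. Section 5.7.3 does not say how its criterion applies to a patient already admitted. The serious adverse event definition in Section 8.2 does, by also covering a prolonged stay.

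**Step 3. What follows from a DLT?**

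| Source | Stated consequence |
|---|---|
| Section 5.7.4 (any DLT) | Accrual, dosing and escalation halt until the SRC has evaluated |
| Appendices 1 and 2, severe and life-threatening | No additional patients dosed; no SRC step stated |
| Appendix 1, recurrent mild or moderate | That patient receives no more drug; nothing said about others |

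Counting Section 5.7.4, the recurrence rule, and the severe and life-threatening entries in each appendix, six statements give three different consequences. Read literally, Section 5.7.4 halts the trial for an event that Appendix 1 handles at patient level.

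**Step 4. Effect on the reported rate.** One event reclassified in a dose group of 3 gives 1/3 = 33.3% instead of 0%. If an optional cohort of 3 at the same dose and regimen is pooled under SAP Section 3.5, it gives 1/6 = 16.7%.

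**Step 5. How likely is a disputed event?** The documents give no rate for these events with ALN-TTR02, so the per-patient risk p is an assumption. The chance of at least one event in n patients is 1 − (1 − p)^n. The planned cohorts hold 4 × 3 = 12 patients; five optional cohorts add 15, for 27.

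| p (assumed) | n = 3 | n = 12 | n = 27 |
|---|---|---|---|
| 1% | 3.0% | 11.4% | 23.8% |
| 5% | 14.3% | 46.0% | 75.0% |
| 10% | 27.1% | 71.8% | 94.2% |

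The conflict does not depend on these figures.

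**The case against.** The strongest reply is that the protocol already contains the risk. The synopsis and Section 10.3 require the SRC to be convened for any potential DLT, and an event that an appendix calls a DLT is surely at least that. Section 4.5.1 has the investigator confer with the sponsor before discontinuing a patient for a serious or intolerable event, with notice to the SRC. Patient 2 cannot be dosed for 48 hours, and Section 8.11 requires serious events to be reported within 24. Section 5.7.4 covers any DLT, so it can be read together with the appendices, which omit the SRC step but do not exclude it. The disputed class is narrow, since many severe reactions would also require hospitalization, and a scheduled stay can ordinarily be told apart from one that a reaction requires. Finally, the appendices are titled as guidelines, while Section 5.7.1 sends readers to Sections 5.7.3 and 5.7.4.

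Much of this stands and reduces the practical impact. Replacement is also largely unaffected for acute reactions, because Section 4.5.2 already bars replacing patients withdrawn for adverse events during infusion. In the SAP the effect is descriptive: the event would still appear in the severe-event and infusion-reaction tables, and only its DLT status would change.

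It does not remove the conflict. SRC opinion is case by case, whereas the appendix rules are automatic, and a site must recognise a potential DLT before the SRC can be convened. Sections 1.6.1 and 5.11 send sites to the appendices, whose DLT sentences are categorical. Even if the appendices simply extend Section 5.7.3, it remains unclear whether their halt is final or awaits SRC review, and whether a recurrent reaction stops one patient or all dosing.

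**Conclusion.** The concern holds and should be corrected. Three reaction types are automatic DLTs in the appendices but missing from Section 5.7.3 and the synopsis, and three different consequences are stated. Life-threatening reactions have the same DLT status everywhere; only their stated consequence differs. A single disputed event shifts the reported DLT rate in its dose group by 33 percentage points (n = 3) or 17 (n = 6).

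This rests on the current protocol text, not on the change summaries. The SRC charter and Figure 5-1 were not available and could contain clarifying text; nothing in the protocol or SAP text available says which passage prevails. The event risks of 1% to 10% are assumptions and carry no weight in the conclusion. The weight comes from where the conflict lies: safety is the primary objective, and this is the rule that stops dosing.

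**What to change.** - Reconcile Sections 5.7.3 and 5.7.4, the synopsis and Appendices 1 and 2 into a single DLT list with a single stated consequence, saying explicitly whether SRC evaluation applies.
- Have the within-cohort dosing condition (Sections 3.1 and 5.7.1, the synopsis and SAP Section 1.2.1) and both appendices refer to that list.
- State how the hospitalization criterion is judged during the planned inpatient stay, and how it relates to the Section 8.2 wording.
- Have SAP Section 4.5.2 and Table 14.3.2.4 use the same list.

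Which reactions count as DLTs, and what follows from one, is for the sponsor and the SRC to decide; this review takes no position on it.

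The cost is a protocol wording amendment, alignment of the SRC charter and a SAP cross-reference. No new data or patients are needed.

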#### 4.5.1 Reasons for Withdrawal

The Investigator may withdraw a patient from the study if the patient:

- Is in violation of the protocol.
- Experiences a serious or intolerable AE (including infusion reactions).
- Experiences a DLT (see Section 5.7.3).
- Develops conditions listed in the exclusion criteria during the course of the study.
- Becomes pregnant.
- Requires a prohibited medication (see Section 5.10).
- Requests to be withdrawn from the study.

The Investigator will also withdraw the patient from the study upon the request of Alnylam or the SRC, or if Alnylam terminates the study. Upon occurrence of a serious or intolerable AE, the Investigator will confer with Alnylam before discontinuing the patient, and the SRC will be notified. A patient may withdraw consent to participate in the study at any time.

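### Appendices 1 and 2 declare three infusion-reaction events to be DLTs that the DLT definition gating first doses of Patients 2 and 3 does not name

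*Protocol*

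**What the plan says.** Protocol 5.7.3 and the Synopsis list four kinds of DLT: life-threatening toxicity, a liver-test threshold, "An infusion reaction that requires hospitalization, despite premedication", and any other toxicity that the SRC judges to rule out further dosing.

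The appendices on managing infusion reactions add their own DLT statements.

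- Appendix 1, mild or moderate acute reaction: "If reaction recurs with re-challenge this patient, this will be a DLT and the patient will receive no further study drug".
- Appendix 1, severe acute reaction: "If a severe acute reaction occurs in any patient, this is a DLT and no more patients will be dosed".
- Appendix 2, severe delayed reaction: "If severe reaction occurs in any patient, this is a DLT and no more patients will be dosed".
- Both appendices also call a life-threatening reaction a DLT and end dosing of further patients.

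Within a cohort, Protocol 5.7.1 releases the next doses as follows: "if the dose is well tolerated, per Section 5.7.3 (Dose-limiting Toxicity), Patients 2 and 3 will receive their first dose". The Synopsis, Protocol 3.1 and SAP 1.2.1 repeat this gate with the same reference. The DLT entry among the withdrawal reasons in 4.5.1 also cites 5.7.3, and a note to the escalation scheme reads "Dose-limiting toxicities are described further in Section 5.7.3, and study stopping rules are described in Section 5.7.4". None of these places refers to an appendix.

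The stopping rule in 5.7.4 begins "For any DLT, accrual to that dose level will stop, all dosing will be discontinued, and dose escalation will end" and makes the halt provisional on SRC evaluation.

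**The concern.** Two parts of the same protocol give different answers to whether an event is a DLT, and the part that controls the next first dose has the shorter list. The clearest case is a severe acute reaction in the first patient of a cohort. Appendix 1 makes it a DLT automatically and halts dosing of further patients. Section 5.7.3 does not name it, and Patient 2 becomes eligible for dosing 48 hours after Patient 1.

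At stake is whether a safety halt is applied in the same way at up to 10 centers, in a study whose primary objective is safety and tolerability. The number of patients reported with a DLT also depends on which text was used, but that is secondary.

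**Working it through.** No sample size, power or error rate is involved. The check compares the two sets of DLT statements and then follows the gate.

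**Step 1. Match each appendix statement to 5.7.3 and the Synopsis.**

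| Event called a DLT in the appendices | Named in 5.7.3 and the Synopsis? | Stated consequence in the appendix |
|---|---|---|
| Recurrence on re-challenge (App. 1) | No | That patient stops |
| Severe acute (App. 1) | No | No further patients dosed |
| Life-threatening acute (App. 1) | Yes, first entry | No further patients dosed |
| Severe delayed (App. 2) | No | No further patients dosed |
| Life-threatening delayed (App. 2) | Yes, first entry | No further patients dosed |

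Five statements, less the two covered by the life-threatening entry, leaves 5 − 2 = 3 that are not named.

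**Step 2. Ask whether the hospitalization entry captures those three.**

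- *Severe acute.* Protocol 5.6 keeps every patient in hospital for at least 24 hours after each infusion. The treatments that Appendix 1 gives for a severe reaction (more than 1 L saline, oxygen above 5 L/min, adrenaline, glucocorticoids) can all be given in that time. Whether such a reaction required hospitalization is then unclear. The serious-event definition in 8.2 also counts a prolonged stay, but the DLT entry does not mention prolongation.
- *Severe delayed.* Appendix 2 grades severity by the intervention needed, and glucocorticoids are among those listed. Section 5.11 sends patients home with medication for delayed reactions that may include oral corticosteroids. A reaction could arguably be severe under Appendix 2 with no admission.
- *Recurrence.* A mild or moderate reaction that returns on re-challenge need not require hospitalization.

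The fourth entry of 5.7.3 could capture all three, but only after an SRC opinion. The appendices need none.

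**Step 3. Time the gate against the scheduled SRC review.** Using the minimum spacings in 5.7.1, with Patient 1's first dose at hour 0:

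- Patient 2: hour 48.
- Patient 3: 48 + 48 = hour 96.
- Earliest time at which 96 hours of post-dose data exist for all three: 96 + 96 = hour 192.

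No SRC review is scheduled before the first doses of Patients 2 and 3. At those points the 5.7.3 criterion is the working check.

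**Step 4. Count the doses that the explicit gate controls.** It covers the first doses of Patients 2 and 3 in each cohort: (4 planned + 5 optional) × 2 = 18 at most. The sentence on second doses asks for 48-hour spacing and does not cite 5.7.3.

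**Step 5. Compare the consequences.** For severe reactions the appendices halt dosing without qualification, while 5.7.4 halts it pending SRC evaluation. For recurrence, Appendix 1 states a result for that patient only, while 5.7.4 read with the DLT label halts everyone. Adding events to 5.7.3 would settle the definition but not these two differences.

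**The case against.** The best defense is that nobody managing an infusion reaction would work from 5.7.3 alone. Section 1.6.1 points to 5.11 and both appendices, and 5.11 points to Appendix 1 for acute and Appendix 2 for delayed reactions. Staff following the severe-reaction guidance would meet the DLT statement there. The SRC must convene for any potential DLT (Synopsis and 10.3), it includes every principal investigator or a designee, and it is notified of serious or intolerable adverse events (4.5.1). Its charter is not among the documents and may settle the matter.

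Much of this stands, and it lowers the chance of an error. It does not remove the conflict. Convening depends on someone recognizing a potential DLT, and the list that the gate tells them to consult omits these events. The protocol presents the appendices as guidelines and does not say which text prevails.

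Three stronger readings are tempting, and the documents do not support them.

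- A reader might infer that the stopping rule itself fails to cover the appendix events. Section 5.7.4 applies to any DLT and does not cite 5.7.3, so it can be read to include them.
- A reader might infer that every planned infusion is affected. Total exposure does not measure the discrepancy. It matters only if one of the three events occurs, and the explicit gate is limited to the doses counted above.
- A reader might infer that the safety tables would hide events. SAP 4.5.2 counts any treatment-emergent event considered a DLT, and it tabulates severe events and infusion-related reactions separately (Tables 14.3.1.4 and 14.3.1.7). One count could shift, but the event would still be reported.

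**Conclusion.** This is an internal inconsistency in a safety rule, and it should be corrected. Three of the five appendix DLT statements have no named counterpart in 5.7.3 or the Synopsis, and the gate for first doses of Patients 2 and 3 cites 5.7.3 only. The practical exposure is narrow: a severe acute reaction that is treated within the planned inpatient stay, followed by dosing of the next patient at 48 hours by a site that applies the gate as written. The current text gives no infusion-reaction rate for ALN-TTR02, so how often this might arise cannot be stated.

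The conclusion assumes that a reaction managed inside the mandatory stay is not automatically one that requires hospitalization, and that the SRC charter does not already reconcile the two lists. If the charter does so, the protocol wording should still agree with it.

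**What to change.** 1. In 5.7.3 and the Synopsis DLT list, add an entry: 'Any severe acute or severe delayed infusion reaction (Appendices 1 and 2)'.
2. In the severe and life-threatening entries of Appendices 1 and 2, replace the unqualified halt on dosing further patients with 'Section 5.7.4 applies'. The stop is then the same in both places, pending SRC evaluation.
3. For recurrence on re-challenge, the sponsor should choose. Either list it in 5.7.3 as a DLT to which 5.7.4 applies, or remove the DLT label from Appendix 1 and keep it as a stop for that patient only. Under the first option even a mild recurrence pauses the whole study, so this choice is the sponsor's to make.

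The cost is wording in four places (5.7.3, the Synopsis and the two appendices), with no new data, visits or assessments. The downside is that a severe reaction pauses all dosing until SRC review, but the appendices already require at least that.
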